Develop participant process/feedback measures. Participant process/feedback measures will be developed. Participants will be asked for their feedback regarding their experiences in the using a semi-structured post-treatment interview. Participants will be asked to share their impressions of each session (e.g., focused on content, length, personal relevance) and of the overall cohesion across therapy sessions. Questions regarding the acceptability of all study activities will be asked in addition to suggested changes for the future trial. Relevant revisions will be made to the manuals and protocol based on this feedback, and a session feedback form will be created to assess the helpfulness and relevance of session topics.

Specific Aim 2: Conduct a pilot RCT comparing remotely -delivered CBTi-CB to remotely -delivered

SE. The second aim of the study is to conduct a pilot randomized trial of CBTi-CB vs. SE (N = 60). This approach is pragmatic and real-world in nature, as both conditions will be delivered remotely to individuals who report using cannabis for insomnia, yet suffer at least mild insomnia. Participants for the RCT phase will be recruited in various ways, including from two Michigan licensed cannabis provisioning centers (OM of Medicine and Bloom City Club), online at UMHealthResearch.org, in the community via flyers, on social media, and at community events. Participants will be randomized to CBTi-CB or SE and undergo self-reported assessments of sleep/insomnia, substance use, and functioning before and after treatment (~8 weeks) and at 16-week follow-up. As many subjects as possible will also undergo objective sleep assessment with actigraphy, if feasible. The ultimate goal is to use this pilot study to provide all of the necessary elements to conduct a future fully-powered RCT comparing these two conditions. To ensure the rigorous conduct of this study, we will utilize the CONSORT checklist and flow diagram to document participant accrual, flow and retention at all stages of the study.

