A scale will be developed that includes items assessing non-therapeutic or “contaminating” therapist behaviors (e.g., use of confrontational strategies, blaming); this scale will be a component of the measurement of therapist skill/competence for CBTi-CB and will be the primary measure of therapist skill/competence for SE. Twenty-five percent of session tapes will be double-coded using the Adherence and Competence scales. We have used similar procedures in prior intervention studies, which have resulted in instruments with sound psychometric properties.

Data Analysis. Data will be examined using standard univariate summary measures and bivariate statistical measures of association, as well as graphical displays. Tests for linearity, independence, missingness, and distributional assumptions (e.g., normality) will be conducted on key variables for each assessment. Distributions will be examined to guide modeling decisions.

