Consistent with Stage 1B research, the primary goals for the pilot RCT are to obtain information about the feasibility of the proposed RCT and estimate the distribution and variability of primary and potential mechanistic outcomes within intervention and control conditions. Initial analyses will involve calculating the attrition rates for 6- and 18-week follow-up assessments in each study group and identifying predictors of drop-out. We will also quantify session attendance and note the percent of participants who did not complete all sessions to identify ways to decrease drop-out and non-compliance to the intervention. Additionally, we will examine all participant feedback from the *Session Feedback Forms* and descriptive data from the measures of treatment integrity and therapist fidelity measures. To examine treatment integrity and fidelity (*the Session-Specific Adherence Rating Scales* and the *Therapist Skill/Competence scale*), inter-rater reliability will be examined with Yule’s Y statistic, by contrasting therapist results with those of the raters, as well as by contrasting those of the two independent raters. The items will be summed to produce overall competency summary scales. Cronbach’s alpha will be used to examine the internal consistency of each summary scale separately for the therapist and raters. The items and rating scales (anchors) will be further refined (added, eliminated or modified), if necessary, based on discussion of face validity and analysis of item appropriateness. These items will be used to monitor therapist skill and fidelity to the intervention protocol and to maintain the integrity of the intervention.

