The primary outcomes of interest include insomnia severity, functioning, and frequency of cannabis use. Potential mechanisms of the intervention include sleep-related behaviors (e.g., changes in time in bed, regularity of sleep schedules) and sleep-related cognitive factors (e.g., changes in sleep-related beliefs, self-efficacy to manage sleep without cannabis, motivation to use cannabis to manage sleep). Based on recent guidelines for Stage 1B research, we will calculate means and standard deviations for primary and mechanistic measures at baseline, post-treatment, and follow-up, as well as change scores for the CBTi-CB and SE groups. In line with recent recommendations for analysis of data from pilot studies, we will focus on estimation of confidence intervals for between-group differences at baseline and all follow-ups.

Moreover, although we recognize that the proposed project will not have adequate power to serve as a definitive study of intervention effects, to prepare for analyses for the future large-scale definitive trial we will compare the outcomes between the two study groups. We hypothesize that intervention participants will have less severe insomnia, better functioning, and lower frequency of cannabis use at follow-ups. The primary outcomes are hypothesized to meet the assumptions of continuous variables, and we will consequently use t-tests to make comparisons. If, however, the distribution of a measure is skewed, alternative modeling strategies (e.g., Poisson regression) will be used. We will examine separate models by sex (i.e., stratified analyses). We will also conduct exploratory analyses of how potential mediators (e.g., self-efficacy) relate to changes in insomnia and cannabis use, and will examine whether changes in insomnia and cannabis use are correlated. Although our sample size is not sufficient to conduct formal mediation analysis, results will inform the identification of those variables that best capture the mechanisms for intervention effects. We will use an intent-to-treat framework.

HUMAN SUBJECTS CONSIDERATIONS

For all phases of this study, approval will be obtained from the Institutional Review Board at the University of Michigan. This research is also covered by a Certificate of Confidentiality from NIDA.

Specific Aim 1-Phase 1: Qualitative Interviews

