Modified Marijuana Motives Questionnaire (MMQ)		X			
Medical Marijuana Use		X			
Prescription Misuse (BOYD)		X		X	X
Side Effect Checklist (SECL)		X		X	X
Marijuana withdrawal checklist revised (MWC-R)		X		X	X
PEG Three-item Scale Assessing Pain Intensity and Interference		X		X	X
BRFSS Model 16(Marijuana Use Type)		X		X	X
Multidimensional Fatigue Inventory (MFI-20)		X		X	X
Epworth Sleepiness Scale		X		X	X
Therapy Evaluation Questionnaire		X		X	
Working Alliance Inventory-SR				X	
Daily Sleep/Wake Diary		X	X	X	X
Actigraphy		X		X	X
Session Attendance			X	X	

Primary outcomes: The ultimate goal is to use this pilot study to provide all of the necessary elements to conduct a future fully-powered RCT comparing these two conditions. We hope to assess the acceptability and feasibility of RCT procedures to determine the distribution and variability of the primary outcomes (insomnia

severity). This will be measured by the change from baseline Insomnia Severity Index score to the score at study completion.

All remuneration for the study will be in the form of gift cards or cash. Participants will be remunerated with a \$40 for the completion of baseline assessment, \$40 for completion of each follow-up assessment, \$20 for completing four out of seven days of the daily online survey for every week before the first follow up and \$10 for completing four out of seven days of the daily online survey for the week before the 2nd follow up, plus an additional \$10 incentive for a urine drug screen at both follow ups. Participants will also receive \$30 to compensate them for any potential charges related to the use of their technology. Participants who do not complete all therapy sessions will still receive the \$30 to cover technology costs, however, they must have completed at least one phone session.

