Exclusion criteria. (1) individuals who do not understand English; (2) individuals judged unable to provide informed consent (e.g., intoxication, mental incompetence, psychosis, bipolar disorder); (3) diagnosis or high suspicion of a sleep disorder other than insomnia based on validated self-report measures; (4) self-reported cancer; (5) self-reported pregnancy; (6) self-reported rotating or night (3rd) shift work; (7) resides a distance greater than 50 miles from Ann Arbor. Participants will not be excluded if they are taking prescription or over the counter medications for sleep, however they will need to report being stable on the medications for at least 8 weeks and agree to maintain the same regime throughout the study. Those who have been taking prescription medications for sleep for less than 8 weeks, or who report they are unable to continue with their medications for the duration of the study (approximately 16-18 weeks) will be excluded.

Research staff will use their clinical judgment to assess cognitive ability to consent. If necessary, recruitment staff may require a potential participant to pass a brief mental status exam. Potential participants may be excluded based on participant best interest (e.g., adult patient with a legal guardian; or if study staff know a patient or their family personally, in order to fully ensure participant privacy), with PI approval.

Justification for selection criteria. Participants in this study will be 21 years old and older for several reasons. First, although state law does allow individuals under the age of 18 to obtain cannabis for medical purposes with consent of a legal guardian, available data indicate that very few adolescents have been issued medical cannabis cards in Michigan. In addition, with the new recreational marijuana laws allowing non-medical use of cannabis, we are not solely recruiting medical cannabis users. This new law states all recreational marijuana uses must be 21 years or older to possess or use marijuana. Therefore, all participants should be age 21 years or older to follow Michigan recreational marijuana laws.

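### The ISI contrast is not settled between change and follow-up score, and the planned t-tests leave out pre-treatment scores that would, on average, give modestly narrower intervals

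*Combined protocol and SAP*

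**What the plan says.** The Data Analysis text under Specific Aim 2 names insomnia severity, functioning and frequency of cannabis use as primary outcomes. It plans means and SDs at each assessment and change scores by arm, then says "we will focus on estimation of confidence intervals for between-group differences at baseline and all follow-ups". The directional hypothesis is also at the visits: "We hypothesize that intervention participants will have less severe insomnia, better functioning, and lower frequency of cannabis use at follow-ups". The comparison is "The primary outcomes are hypothesized to meet the assumptions of continuous variables, and we will consequently use t-tests to make comparisons". Another model is named only for skewed measures, and sex enters only through separate stratified models.

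The Primary outcomes paragraph of the RCT section defines ISI differently: "This will be measured by the change from baseline Insomnia Severity Index score to the score at study completion". Study completion is not formally tied to a visit there. The actigraphy text under the RCT Recruitment Procedures, however, places the final follow-up at approximately 16 weeks, and ~16 weeks is the last column of the RCT assessment table.

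That table schedules ISI at screening, and SF-12 and Timeline Follow Back at baseline; all three are repeated at ~8 and ~16 weeks. Randomisation is blocked on gender.

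On timing, the Specific Aim 2 overview has assessments "before and after treatment (~8 weeks) and at 16-week follow-up", while the Data Analysis text speaks of "calculating the attrition rates for 6- and 18-week follow-up assessments in each study group".

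**The concern.** A t-test on the follow-up score fixes the baseline coefficient at 0, and a t-test on change fixes it at 1. Neither estimates it. The two estimates differ by exactly the chance baseline difference between arms, so an analyst can follow the plan faithfully with either quantity and report a different ISI effect. The plan gives its emphasis to interval estimation and says the between-arm comparison is preparation for the definitive trial's analyses, so it should fix which contrast the interval describes. A model that estimates the baseline coefficient also tends to give a narrower interval from data already being collected.

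The sentence "Distributions will be examined to guide modeling decisions" does not fill the gap. It concerns the shape of the outcome, not covariates, and the only alternative modelling named is for skewness.

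**Working it through.** The documents give no SD, correlation, effect size or interval width for ISI, so there is no planned figure to reproduce. The check compares expected 95% interval half-widths.

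**Inputs**
- 30 per arm (Specific Aim 2).
- Entry requires ISI >10 (RCT Inclusion criteria). Assumed to remove the lowest 25% or 50% of a normal distribution.
- Pre-selection baseline/follow-up correlation r: assumed 0.3 to 0.7.
- Unit: the pre-selection SD of ISI. Follow-up = r × baseline + error, with error variance 1 − r².

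**Baseline variance V after the entry rule.** V = 1 + aλ − λ², where a is the normal cut-point and λ = φ(a)/(share kept).
- Lowest 25% removed: a = −0.674, λ = 0.424, V = 0.535.
- Lowest 50% removed: a = 0, λ = 0.798, V = 0.363.

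**Half-widths**
- Follow-up t-test: 2.002 × √[(2/30)(r²V + 1 − r²)]
- Change t-test: 2.002 × √[(2/30)((1 − r)²V + 1 − r²)]
- Baseline-adjusted: 2.002 × √[(2/30)(1 − r²)(1 + 1/56)]. The last factor charges the model for chance baseline imbalance; the t quantile has 57 rather than 58 degrees of freedom.

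Example, r = 0.5 and V = 0.535: either t-test has variance 0.25 × 0.535 + 0.75 = 0.884 and half-width 0.486. The adjusted half-width is 0.452. Ratio 1.075.

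| r | Removed | Follow-up | Change | Adjusted | Follow-up wider by | Change wider by |
|---|---|---|---|---|---|---|
| 0.3 | 25% | 0.506 | 0.560 | 0.498 | 1.7% | 12.4% |
| 0.5 | 25% | 0.486 | 0.486 | 0.452 | 7.5% | 7.5% |
| 0.7 | 25% | 0.454 | 0.386 | 0.373 | 21.9% | 3.7% |
| 0.3 | 50% | 0.502 | 0.539 | 0.498 | 0.8% | 8.3% |
| 0.5 | 50% | 0.474 | 0.474 | 0.452 | 4.9% | 4.9% |
| 0.7 | 50% | 0.429 | 0.381 | 0.373 | 15.1% | 2.2% |

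Simulation (20,000 trials per setting) gives the same ranges: about 2-12% for change and 1-22% for follow-up scores. With 24 per arm (an assumed 20% lost at random) the ranges are unchanged.

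**Break-even.** At r = 0.2 the follow-up/adjusted ratio is 1.002 (25% removed) or 0.998 (50% removed). At r = 0.1 it is 0.993, so the adjusted interval is 0.7% wider.

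**Change versus follow-up estimate.** The difference is the baseline imbalance, with SD √(2V/30) = 0.189 or 0.156. The 95% ranges are 1.96 × 0.189 = ±0.37 and 1.96 × 0.156 = ±0.305.

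**How often the two t-intervals disagree on excluding zero** (simulated, same r and entry-rule settings):

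| True effect (SD) | Share of trials |
|---|---|
| 0 | 5-8% |
| 0.30 | 14-26% |
| 0.60 | 17-24% |
| 1.20 | about 1% or less |

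**Gender.** If it explained 5% of residual variance, omitting it would widen the interval by 1/√0.95 − 1 = 2.6%; if it explained none, 0%. This is minor.

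**The case against.** The strongest reply is that the t-tests are valid, the trial is a pilot whose primary goals are feasibility and variability, and the gain is small and rests on an assumed r. Most of that stands. For change, the quantity the Primary outcomes paragraph names, the loss is 2-12%. For follow-up scores at r = 0.3 it is 1-2% on average, and in single simulated datasets the t-interval is the narrower one in 37% to 47% of cases. ISI is taken at screening, and online screeners have their baseline appointment scheduled later, which could lower r. What remains is that the adjustment costs almost nothing, and that the change/follow-up conflict needs no assumption about r.

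Three stronger readings are tempting, and the documents do not support them.

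- *The analyst may choose between 8 and 16 weeks.* The ~16-week visit is already called the final follow-up, and intervals are planned at all follow-ups, so both visits will be reported. Study completion needs a one-line definition.
- *The definitive trial would lose what it needs.* SDs are planned at each assessment, with change scores. Given the SDs s₀, s₁ and s_d (baseline, follow-up, change), r = (s₀² + s₁² − s_d²)/(2s₀s₁), and the adjusted SD is s₁√(1 − r²). The information is largely recoverable.
- *The two t-tests would often contradict each other.* That depends on an unknown effect, as the table shows, and excluding zero is not the plan's stated focus.

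**Conclusion.** The point holds as a modest one. The plan gives two descriptions of the ISI contrast and does not say which one the t-test uses, and it plans no baseline adjustment although the values will be in hand. Neither t-test is biased under randomisation. On average they are less precise than an adjusted model: about 2-12% wider intervals for change and 1-22% for follow-up scores, given 30 analysed per arm, r of 0.3 to 0.7 before selection and 25% to 50% removed by the entry rule. There is no gain over the follow-up t-test at r of about 0.2 or below, and little at 0.3. The two unadjusted estimates differ by a 95% range of about ±0.305 to ±0.37 pre-selection SD.

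The 6- and 18-week timing is a genuine inconsistency, but it sits in the attrition sentence and does not by itself change the ISI contrast. The change is worth making because it is cheap; the pilot's conclusions do not hang on it.

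**What to change.** 1. In the Specific Aim 2 Data Analysis text, replace the pooled t-tests with a linear model of the follow-up score on arm, pre-treatment score and gender stratum at each visit, and report adjusted differences with 95% intervals. A mixed model over both visits with the same covariates is an acceptable alternative. Carry the covariates into any model used for a skewed outcome.
2. There and in the Primary outcomes paragraph, name this adjusted difference as the ISI contrast, with the screening ISI as the pre-treatment score. State that study completion is the ~16-week visit already called the final follow-up, and label ~8 weeks secondary.
3. Reconcile the 6- and 18-week attrition timing with the ~8 and ~16 weeks in the Specific Aim 2 overview, the actigraphy text and the RCT assessment table.

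The cost is wording and one model per outcome, with no new data, visits or forms. The model spends two degrees of freedom and loses under 1% of precision if r is near zero.

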Specific Aim 2: Conduct a pilot RCT comparing CBTi-CB (n=30) to SE (n=30) delivered remotely to (a) assess the acceptability and feasibility of RCT procedures; (b) determine the distribution and variability of the primary outcomes (insomnia severity, health-related functioning); and (c) assess potential mechanisms of change (sleep-related behaviors; sleep-related beliefs; sleep self-efficacy; and cannabis use motivation) within the CBTi-CB and SE conditions.

The proposed project addresses a key objective articulated in the most recent **NIDA Strategic Plan**, specifically, to “develop and test novel treatments based on the science of addiction” (Objective 3.1). This work is significant because of the large and growing number of US adults who use cannabis to manage their insomnia. Given the extent of daily cannabis use in users of cannabis for insomnia, intervening on sleep in this group represents the opportunity to engage and improve outcomes in those with heavy cannabis use. The study is innovative because it targets insomnia, a highly comorbid condition in a group of non-treatment seeking individuals, and proposes that improvement in sleep will reduce cannabis use and improve health-related functioning. The impact is enhanced by leveraging telemedicine approaches to optimize reach of the treatment.

RESEARCH DESIGN AND METHODS

Overview of approach. The purpose of this project is to adapt, iteratively refine, and pilot test an existing CBTi intervention for use in adults who currently use cannabis for insomnia (CBTi-CB). The proposed work is consistent with Stages IA/IB of the NIH Stage Model of Intervention Development.^{20,21} Also in line with these recommendations, the pilot trial will gather data on the extent to which participation in the CBTi-CB intervention is associated with changes in the proposed mechanisms of action of the intervention.^{20,21} The proposed project has two primary aims: (1) adapt and iteratively refine remotely-delivered CBTi-CB to address the unique needs of individuals using cannabis for insomnia and develop and refine a matched remotely-delivered Sleep Education Control (SE) condition; and (2) conduct a pilot randomized controlled trial (RCT) comparing remotely-delivered CBTi-CB to SE to (a) assess the feasibility of RCT procedures; (b) determine the distribution and variability of the primary outcomes (insomnia severity, health-related functioning); and (c) assess potential mechanisms of change.

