Following completion of data collection during the baseline assessment, participants will be randomized to a treatment condition – Sleep Hygiene Education (SHE; n=30) or Cognitive Behavioral Therapy for adults who currently use cannabis for insomnia (CBTi-CB; n=30). Randomization to condition will be carried out blocking on gender (male versus female). Participant responses to questions based on gender obtained during baseline will be utilized to select the appropriate block for randomization. Research staff will confirm the participant responses before beginning the randomization procedures. "Gender" for randomization purposes will be operationalized as the gender the participants indicated they were assigned at birth; however, additional questions regarding the gender the participant identifies with will also be collected. Should a participant decline to answer a key blocking variable during the survey administration, research staff will verbally ask clarification questions to determine block assignment. If a participant refuses to provide information that allows for the possibility of blocking they will be excluded from participating further in the study.

Computerized randomization will occur in blocks of randomly chosen sizes in order to equalize randomization over time and to prevent the possibility that staff could unwittingly manipulate subject assignment to conditions. The study biostatistician will complete the treatment allocation sequence process prior to the start of

recruitment for the study. Staff members who will be involved in the enrollment process will not be included in the randomization sequencing process. To further avoid manipulation of condition, randomization will not be determined until after all baseline data collection activities have been completed. We will utilize allocation concealment procedures to ensure that that research staff member enrolling the participant will not know in advance which treatment the next person will receive.

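### Sex is the randomisation stratum, but the between-arm t-tests omit it, and the separate models by sex come with no planned between-sex contrast

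*Combined protocol and SAP*

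**What the plan says.** The pilot compares two arms of 30: "Conduct a pilot RCT comparing CBTi-CB (n=30) to SE (n=30) delivered remotely" (Objectives, Specific Aim 2).

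Under Human Subjects Considerations, Specific Aim 2, Recruitment Procedures: "Randomization to condition will be carried out blocking on gender (male versus female"). For this purpose gender is "operationalized as the gender the participants indicated they were assigned at birth", so the stratum is in effect sex.

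The Data Analysis text for Specific Aim 2 (Research Design and Methods) gives the between-arm method: "The primary outcomes are hypothesized to meet the assumptions of continuous variables, and we will consequently use t-tests to make comparisons". The fallback is: "If, however, the distribution of a measure is skewed, alternative modeling strategies (e.g., Poisson regression) will be used". Neither sentence mentions sex. Sex then appears once: "We will examine separate models by sex (i.e., stratified analyses"). No arm-by-sex term, no difference between the two sexes' effects and no rule for reading the two sets of results is given. The same section states its emphasis: "we will focus on estimation of confidence intervals for between-group differences at baseline and all follow-ups".

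**The concern.** Two features of the plan do not fit the design.

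First, blocking on sex balances the arms for sex. If sex predicts the outcome, that balance makes the treatment difference more precise, but an ordinary two-sample t-test does not credit the gain. Its standard error still contains the variation between the sexes. Interval width and outcome variability are among the things this pilot is meant to pass on to the later trial.

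Second, fitting one model per sex produces two effects and two p-values. The quantity that bears on whether the effect differs by sex is the difference between those effects, with its own interval, and the plan does not ask for it. Without it, the easy reading is that one sex responded and the other did not. At this sample size that pattern can arise by chance when the true effect is the same in both, and it could influence the design of the later trial.

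**Working it through.** **Inputs from the documents.** 60 participants, 30 per arm; randomisation blocked on sex assigned at birth; t-tests between arms; separate models by sex.

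**Inputs the documents do not give, so assumed.** Two-sided 0.05; effect size d in SD units, 0 to 1.2; males and females per arm 15:15, with 10:20 as an uneven case; no dropout, or 20% (12:12 per arm). The plan states no power or precision figure, so there is none to reproduce.

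**Step 1: cost of leaving sex out of the t-test.** Let g be the difference in mean outcome between the sexes, in within-sex SDs. With 15 of each sex per arm, the variance used by the t-test is inflated by 1 + (g²/4)(30/29). Apart from a negligible change in the t quantile (58 to 57 df), the interval is too wide by the square root of this.

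| g | √(1 + (g²/4)(30/29)) | Simulated width ratio | Simulated type I error, t-test without sex |
|---|---|---|---|
| 0.3 | √1.023 = 1.012 | 1.011 | 4.7% |
| 0.5 | √1.065 = 1.032 | 1.03 | 4.3% |
| 0.8 | √1.166 = 1.080 | 1.079 | 3.5% |
| 1.0 | √1.259 = 1.122 | 1.122 | 3.0% |

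The simulations used 50,000 runs. With sex in the model the type I error was 4.9–5.2%. At d = 0.65 and g = 0.5, power was 67.6% without sex and 69.8% with it.

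**Step 2: precision of the sex comparison (15:15).** 95% half-widths in SD units:

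- Overall effect: 2.002 × √(2/30) = 2.002 × 0.258 = 0.517.
- Effect within one sex, separate model: 2.048 × √(2/15) = 2.048 × 0.365 = 0.748, which is 0.748/0.517 = 1.45 times the overall one.
- Difference in effect between sexes: 2.003 × √(2/15 + 2/15) = 2.003 × 0.516 = 1.034.

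The half-width for the difference rises to 1.10 with a 10:20 split and to 1.16 with 20% dropout. With 15:15, power for a true interaction of 0.5 SD is 16%, and 80% power needs an interaction of about 1.45 SD.

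**Step 3: what reading the two models by significance would do.** Suppose the true effect is the same in both sexes. With power pM and pF from the exact two-sample t-test, the chance that exactly one sex is significant is pM(1 − pF) + pF(1 − pM). For example, at d = 0.5 and 15:15: 2 × 0.262 × 0.738 = 0.387. At d = 0.8 and 10:20: 0.395 × 0.307 + 0.693 × 0.605 = 0.541.

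| d | Power per sex, 15:15 | Exactly one significant, 15:15 | 10:20 | 12:12 (20% dropout) |
|---|---|---|---|---|
| 0 | 5.0% | 9.5% | 9.5% | 9.5% |
| 0.3 | 12.5% | 21.8% | 22.0% | 19.3% |
| 0.5 | 26.2% | 38.7% | 39.8% | 33.9% |
| 0.8 | 56.2% | 49.2% | 54.1% | 49.8% |
| 1.0 | 75.3% | 37.2% | 45.4% | 45.6% |
| 1.2 | 88.7% | 20.0% | 30.0% | 31.7% |

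An arm-by-sex interaction test rejects in about 5% of such trials whatever the common effect (simulated 4.9–5.1%). Among trials where exactly one sex was significant, at d = 0.5 to 1.0, the interaction test was significant in only about 10–12%.

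**The case against.** Three stronger readings are tempting, and the documents support none of them.

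*That separate models cannot show whether the effect differs.* They give two independent estimates with standard errors, and anyone can subtract them. For a continuous outcome, one model with an arm-by-sex term returns the same per-sex point estimates and only pools the residual variance. What is missing is a pre-specified contrast.

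*That the plan will often produce a false sex difference.* The rates in Step 3 require someone to split each sex's result at 0.05 and treat disagreement as effect modification. The plan states no hypothesis about sex, sets no significance rule per sex and puts its emphasis on confidence intervals. The rates also depend on the assumed effect: high in the middle of the range, low at both ends.

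*That omitting the stratum invalidates the main comparison.* It introduces no bias, the error is on the conservative side, and nothing in the documents indicates that sex strongly predicts the outcome.

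It is also fair to say that this is a pilot, that the plan admits it is too small for a definitive test, and that the interaction will be estimated too imprecisely to teach much. All of that stands and limits the size of the point. It does not remove it. The sex models are not labelled exploratory (that label is attached only to the mediator analyses), and the group comparisons are meant to prepare the later trial. A focus on intervals is an argument for reporting the one interval that is absent.

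**Conclusion.** The mismatch is real and modest in its consequences. The randomisation stratum is missing from the planned between-arm comparison, and the sex analysis stops short of the quantity it needs.

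The loss of precision is trivial if the sexes differ little and reaches about 12% of interval width only at a full SD difference, assuming the sexes are balanced within arms. The larger exposure is interpretive and conditional: 9.5% to about 54% of trials would show one significant sex under a common effect, across the effect sizes, splits and dropout considered at two-sided 0.05, and only if results are read that way. The facts about the plan are certain. The size of the harm rests on assumptions the documents do not supply.

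**What to change.** Three changes to the Data Analysis text for Specific Aim 2:

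1. Replace the t-test by a linear model with arm and sex, using the variable that defined the randomisation blocks. Put sex in any Poisson or other fallback model too. Take the headline arm effect and its interval from this model, without the interaction.
2. Replace the separate models by one model with arm, sex and arm-by-sex. Report the interaction with its 95% interval and the per-sex effects from the same model.
3. Label the sex results exploratory and state that no inference will be drawn from comparing per-sex p-values.

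The cost is one degree of freedom for sex and one for the interaction, with no new data. The interaction interval, about ±1.03 SD at 15 per arm per sex and wider with an uneven split or dropout, will be too imprecise to settle whether the effect differs by sex. Reporting it makes that plain.
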